3. The tertiary aim is to explore the preliminary efficacy and the short-term effect of the DSS intervention on diabetes knowledge (Spoken Knowledge in Low Literacy for Diabetes) Appendix, self-efficacy (Self-care of Diabetes Inventory Confidence Subscale), and distress (Problem Areas in Diabetes Scale) at baseline, immediate post-program and 6 weeks post-DSS program, or immediately before release if release from prison is less than 6 weeks post-DSS program.

4. Evaluate the feasibility of a post-session support group (one facility) by documenting potential problems with scheduling, participation, and engagement.

The overall goal of this study is to use the results to inform a pilot study of the effect of a DSS (Diabetes Survival Skills) on clinical (e.g. glycemic control and Cardiovascular measures), psychosocial (e.g. Diabetes Related Stress, Quality of Life), and behavioral (e.g. self-care and adherence) post-release outcomes and to explore the feasibility of adding a support group to the DSS intervention (DSS+).

Reference

1. American Diabetes Association (2016). Standards of medical care in diabetes-2016 abridged for primary care providers. *Clinical Diabetes*. 33, 97–111. doi: 10.2337/dc12-s011

2. Brunisholz, K. D., Briot, P., Hamilton, S., Joy, E. A., Lomax, M., Barton, N., . . . Cannon, W. (2014). Diabetes self-management education improves quality of care and clinical outcomes determined by a diabetes bundle measure. *Journal of multidisciplinary healthcare*, 7, 533.
3. Chrvla, C. A., Sherr, D., & Lipman, R. D. (2015). Diabetes self-management education for adults with type 2 diabetes mellitus: A systematic review of the effect on glycemic control. *Patient education and counseling*.
4. Powers, M. A., Bardsley, J., Cypress, M., Duker, P., Funnell, M. M., Fischl, A. H., . . . Vivian, E. (2015). Diabetes Self-management Education and Support in Type 2 Diabetes A Joint Position Statement of the American Diabetes Association, the American Association of Diabetes Educators, and the Academy of Nutrition and Dietetics. *The Diabetes Educator*, 41(4), 417-430.
5. Fan, L., & Sidani, S. (2009). Effectiveness of Diabetes Self-management Education Intervention Elements: A Meta-analysis. *Canadian Journal of Diabetes*, 33(1), 18-26. doi: [http://dx.doi.org/10.1016/S1499-2671\(09\)31005-9](http://dx.doi.org/10.1016/S1499-2671(09)31005-9)

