The proposed study is guided by the Information-Motivation-Behavioral skills (IMB) model^{28, 29} of health behavior change. The IMB model posits that a person needs accurate information about the health behavior, personal and social motivation to act on the information, and the behavioral skills to correctly perform the behavior²⁸ The IMB model has been used widely to inform health behavior change interventions for improving adherence to treatment among persons with HIV and more recently to enhance diabetes knowledge, motivation and behavioral skills for Latinos with diabetes. In a study with Latinos with diabetes, Osborn et al.²⁹ found that diabetes knowledge (knowledge), fatalistic attitudes (personal motivation), and social support (social motivation) were significant direct predictors of diabetes self-care and through behavior were related to glycemic control.

The proximal outcomes of interest for the current study include diabetes knowledge (information), outcome expectancies (personal motivation), self-efficacy (behavior skills), peer support (evaluated in one facility only) (social motivation) and diabetes related distress which may or may be mediated by peer support and self-efficacy³⁰. Given the small sample size, efficacy testing is limited. The goal is to continue the DSS or DSS+ intervention training and follow releasees out into the community to examine distal outcomes of the IMB model including adherence, and glycemic control.

Table II. IMB based DSS Intervention components

Construct	Operationalized	How Provided
Information	Diabetes Knowledge	
 Interaction with APRN/PI expert in providing DSME. Focus on Diabetes Survival Skills. Selected Low Literacy Patient Education Pamphlets from the Partnership to Improve Diabetes Education (PRIDE) study³¹ (Attachment 3)
Motivation	Support Group (for two groups) Outcome Expectancies	
 APRN/PI to facilitate using motivational interviewing techniques. Discussion of benefits of self-care
Behavioral skills	Self-efficacy	
 Workbook Questions based on Diabetes Survival Skills found in the

		
Diabetes Education Prompt Pack ³² (AADE,2016).
 
 Return Demonstration/Simulation: Performing Finger sticks for Blood Glucose Monitoring, Insulin Administration, Documentation in Log Book, Food Selection, Hypoglycemia management.

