Design: The proposed study will examine the feasibility, acceptability and preliminary efficacy measures of a quasi-experimental non-equivalent control group 6-week intervention study with repeated measures at baseline, 6 weeks, and 12 weeks. Acceptability of the DSS intervention will be examined using a qualitative descriptive design with focus group interviewing.

Prior to data collection, IRB approval from the University of Connecticut and the CDOC Research Advisory Council (RAC) will be obtained. Procedures for the recruitment of inmates with diabetes will be determined in collaboration with the Connecticut Department of Corrections administration (CDOC). Recruitment procedures as described in the prior section have been previously used and approved by the CDOC RAC. The final RAC approval has been obtained (see Connecticut department of Corrections letter of approval). The RAC has reviewed this proposal and granted approval. After UCONN IRB and RAC approval, meetings with the Wardens will be arranged, email communication will be sent to Correctional Managed Healthcare (CMHC) nursing director (Attachment 2), recruitment flyers will be posted in the participating prisons, and the researcher will negotiate dates and times to be available during several Chronic Care Clinic sessions for in person recruitment as described in the recruitment procedures.

The "sick slips" from inmates requesting to hear more about the study will be collected from my assigned mailbox in medical records or another designated location and subsequently reviewed. Prior to scheduling a meeting with the potential participant, the PI will request that the DOC liaison or other designee review the list of potential participants to confirm that the participants meet the secure

classification to participate in groups. If interested potential participants do not meet the security classification, the PI will follow the DOC procedure for notifying participants who do not meet the DOC classification criteria.

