			Measure 1					Measure 2		Measure 3	
Treatment Facility	Group 1 N=24 Group 2 (N=24) (n=12 per DSS session)	Informed consent STOFHLA MoCA Demographics	Baseline Surveys SKILLD ¹ SCODI ² OEQ ³ PAID ⁴ Session 1 Topic Diabetes Intro and Preparing for Discharge	Session 2 Topic Medicine taking	Session 3 Topic Monitoring	Session 4 Topic Hypo-glycemia	Session 5 Topic Basic Meal planning	Session 6 Topic Sick day manage post-release follow-up	Focus Group (2)	Surveys SKILLD SCODI OEQ PAID	Support Group
Control Facility ⁸	Group 1 (N=24) Group 2 (N=24)	Visit 1 Week 1 1.5. hours Informed consent STOFHLA ⁵ MoCA ⁶ Demographic ⁷	Visit 2 Week 4 1 hour Measure 1 Surveys SKILLD SCODI OEQ PAID					Visit 3 Week 9 1 hour Measure 2 Surveys SKILLD SCODI OEQ PAID		Visit 4 Week 15 60 min Measure 3 Surveys SKILLD SCODI OEQ PAID	Visit 5-10 Week 15-20 Optional DSS Sessions 1-6

¹ Spoken Knowledge Low Literacy in Diabetes; ² Self-care of Diabetes Inventory Confidence subscale; ³ Diabetes Outcome Expectancies Questionnaire; ⁴ Problem Areas in Diabetes, ⁵ Short Test of Functional Health Literacy Adults, ⁶ Montreal Cognitive assessment, ⁷ Demographics ⁸ Control group to receive the intervention after week 12.

The exact timing of the support group in the treatment facility will be negotiated with the CDOC but will not start prior to the completion of 12-week data collection time point for group 1 and 2).

Intervention

The DSS sessions will be held in a room in the medical area away from other inmate activities. There will be a correctional officer (CO) present outside of the room at all times and the door of the conference room will be slightly ajar according to the DOC's safety related procedures. The first session of the six sessions will be 90 minutes' duration to allow for completion of the 4 instruments- the SKILLD (Attachment 10), SCODI (Attachment 11), and the PAID (Attachment 12,). OEQ (Attachment 13 note); The PI will read the instruments aloud to the group and collect the surveys before starting the session.

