10. Chlebowy, D. O., & Garvin, B. J. (2006). Social support, self-efficacy, and outcome expectations impact on self-care behaviors and glycemic control in Caucasian and African American adults with type 2 diabetes. *The Diabetes Educator*, 32(5), 777-786

Justification of Sample Size: For qualitative and pilot studies, describe how the proposed sample size is appropriate for achieving the anticipated results. For quantitative studies, provide a power analysis that includes effect size, power and level of significance with references for how the sample size was determined. Explain the rate of attrition, with references as appropriate. Data Analysis: For all studies, provide a description of the statistical or qualitative methods used to analyze the data.

Quantitative:

Demographic data, sociocultural and cognitive function will be analyzed with univariate statistics.

Justification of Sample size: h.

Previous research 24 has demonstrated that, in diabetes behavioral interventions targeting the variable “diabetes knowledge,” an effect size of 0.47-0.68 is achievable at $p < .05$. Therefore, with a moderate effect size ($d=0.50$), $p<0.05$, power 0.80, 2 groups, and an estimated moderate correlation (0.50) between 3 repeated measures, the power analysis 25 indicated a need for 86 participants.

Attrition for DSME programs is reported to range as high as 20- 50%. 2,3. This wide variation and high rate of attrition has been reported as being multifactorial e.g. group versus individual program, accessibility, timing, presence of depression, older age of participant.4,5 Attrition rates for group DSME has been lower than non-group education.5 There is no data on attrition rates for DSME or other similar programs in the prison. Factors possibly influencing attrition in the prison that need to be considered include movement of incarcerated persons between facilities and other restrictions of movement e.g. lockdown. 6 During the PI’s previous research, communication with the facility and CDOC designee was critical to identify real or potential issues affecting data collection. The PI will employ the following strategies to reduce attrition:

1. Confirm with the CDOC designee prior to participant enrollment that the potential participant is within 6-9 months of release to the community.

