Data will be analyzed using SPSS. Descriptive methods will be used to generate summary statistics of demographic and study variables to answer questions 5 about feasibility. We will use the information obtained under Aim 1-3 to further refine the intervention.

Aim 1 Feasibility: Counts, percentiles, measures of central tendency, and correlations will be examined to provide information to address each hypothesis in Aim 1. Additionally, quantitative content analysis using apriori themes from Diabetes Education Prompt Deck 34 from the PIs experience conducting research with incarcerated persons will be used to further assess participant engagement(H3) and intervention implementation(H5).

Aim 2 Acceptability, Qualitative data from each FGI transcript (unit of analysis) will be analyzed with Krippendorff 43method of qualitative content analysis. An iterative process of coding and categorizing the data will be used to identify themes within and across transcripts. Two researchers will read each transcript, several times to come to consensus on themes.

Aim 3 Preliminary efficacy of the effect of the DSS training on the IMB outcome variables will be evaluated with repeated-measures ANOVA and for the assumptions of repeated measures ANOVA.

Qualitative

The Focus Group Interview (FGI) will be guided by the interview guide (Appendix). Focus Groups Interview (FGIs) will be audiotaped with verbatim transcriptions, entered into a password secured Word file and imported into ATLAS/TI software for data management. Qualitative data from each transcript will be analyzed with Krippendorff method of qualitative content analysis. An iterative process of coding and categorizing the data will be used to identify themes within and across transcripts. Two researchers will review each transcript, read each transcript several times to come to consensus on themes.

Justification of Sample size: The rule of thumb is to conduct 4 focus groups and then determine if saturation is reached ⁷ Consensus is lacking in the literature on the total number of participants needed to achieve data saturation but five to eight participants but not more than 10 is usually adequate for most noncommercial topics when using focus group interviewing techniques. ⁷ The PI will enroll 10 participants per group to account for no-shows.

7. Kreuger, K.A. & Casey, M.A. (2009). *Focus Groups a Practical Guide for Applied Research*. 4th ed. Washington DC.

Inclusion/Exclusion Criteria

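### The 86 participants fit only a group main effect that averages in the pre-DSS baseline; at d = 0.50 that term has about 47% power and group-by-time about 66%, not 80%

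*Combined protocol and SAP*

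**What the plan says.** The quantitative part of Justification of Sample Size cites earlier diabetes-knowledge effects of 0.47 to 0.68. It plans "with a moderate effect size ($d=0.50$), $p<0.05$, power 0.80, 2 groups", with an "estimated moderate correlation (0.50) between 3 repeated measures, the power analysis 25 indicated a need for 86 participants". Attrition of up to 10% then takes 86 to the 96 to be enrolled. No model term is named.

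Under Statistical strategy, Aim 3 reads: "Preliminary efficacy of the effect of the DSS training on the IMB outcome variables will be evaluated with repeated-measures ANOVA". Apart from a reference to the ANOVA assumptions, that is all. It names no main effect, interaction, contrast or baseline adjustment.

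The Design paragraph describes a "quasi-experimental non-equivalent control group 6-week intervention study with repeated measures at baseline, 6 weeks, and 12 weeks". For the baseline surveys in the treatment facility, the Intervention section says: "The PI will read the instruments aloud to the group and collect the surveys before starting the session". So one of the three measures precedes any DSS content.

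The plan is modest about efficacy. Under Purpose, "The tertiary aim is to explore the preliminary efficacy and the short-term effect of the DSS intervention on diabetes knowledge" and on the other outcomes. The Theoretical Framework adds: "Given the small sample size, efficacy testing is limited".

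**The concern.** A two-group, three-occasion repeated-measures ANOVA offers two tests that involve group. The main effect compares the arms on the average of all three occasions. Group-by-time asks whether the arms change differently. They answer different questions and have different power.

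The main effect suits this design poorly. DSS cannot alter a measure taken before session 1, so including it dilutes any real effect. Each arm is also a single, non-randomised facility, so a difference that existed beforehand goes straight into the main effect and can look like benefit.

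If that is the term behind the 86, the stated 80% does not apply to a DSS effect of 0.50 SD. If group-by-time is the intended test, the 86 was not derived from it. Either way, a reader of the results cannot tell in advance which test decides whether DSS shows promise, and the overall goal is to use those results to inform the next study.

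**Working it through.** **Inputs from the sample-size section.** d = 0.50, so f = d/2 = 0.25 for two equal groups; alpha 0.05; m = 3 measures; r = 0.50; stated N = 86. Allocation is 48 and 48. Allowing 10% attrition, 86/0.90 = 95.6, hence 96.

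**Reproducing 86.** For the group main effect, λ = N f² m / [1 + (m − 1)r].
- At N = 86: λ = 86 × 0.0625 × 3 / 2 = 8.06 on F(1, 84), power 0.8015.
- At N = 84: power 0.792. So 86 is the smallest even total that reaches 80%.

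Other standard calculations on the same inputs give different totals:

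| Calculation | Total N |
|---|---|
| Group-by-time with f = 0.25 entered directly | 28 |
| t test at one time point, two-sided (one-sided) | 128 (102) |
| Change from baseline to follow-up mean, normal approximation | 96 |
| Baseline-adjusted follow-up mean, normal approximation | 64 |

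That the main effect was sized is therefore an inference from the numerical match.

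**Power for a DSS effect.** Assumed group differences are 0 at baseline and 0.50 SD at both follow-ups, with r = 0.50 between all pairs, independent participants and 43 per arm (N = 86).

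- *Group main effect.* Averaged difference (0 + 0.5 + 0.5)/3 = 0.333. Variance of a three-measure mean (1 + 2 × 0.5)/3 = 0.667. λ = (86/4) × 0.333²/0.667 = 3.58 on F(1, 84): **46.5%**.
- *Group-by-time.* Squared deviations of (0, 0.5, 0.5) from 0.333 sum to 0.1667. λ = (86/4) × 0.1667/(1 − 0.5) = 7.17 on F(2, 168): **65.8%**.
- *Change from baseline to follow-up mean.* Variance 0.75 + 1 − 2 × 0.5 = 0.75. λ = (86/4) × 0.25/0.75 = 7.17 on F(1, 84): **75.4%**.
- *Baseline-adjusted follow-up mean.* Variance 0.75 − 0.25 = 0.50. λ = (86/4) × 0.25/0.50 = 10.75: **90.0%**, given equal baselines.

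Simulation of 20,000 trials gave 46.5% for the main effect and 65.5% for group-by-time.

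| At r = 0.50 | Main effect | Group-by-time | Change contrast |
|---|---|---|---|
| Power at N = 86, d = 0.50 | 46.5% | 65.8% | 75.4% |
| Power at N = 96, d = 0.50 | 50.8% | 71.0% | 79.9% |
| N for 80% at d = 0.50 (noncentral F) | 192 | 118 | 98 |
| Smallest d with 80% at 86 (96) | 0.75 (0.71) | 0.58 (0.55) | 0.53 (0.50) |
| Power at 86, d = 0.47 / 0.575 / 0.68 | 42 / 58 / 72% | 60 / 79 / 91% | 70 / 86 / 95% |

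**Sensitivity at d = 0.50, N = 86.**
- As r goes from 0.3 to 0.7, main-effect power falls from 55% to 40%, group-by-time rises from 51% to 88% and the change contrast from 61% to 93%.
- If the effect fades or builds (0.50 then 0.25, or the reverse), the three powers are 29%, 53% and 51%.

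**Facility difference, illustration only.** The documents give no figure. Assume a stable gap of 0.20 SD and no DSS effect. At N = 86 the main effect then rejects about 20% of the time, the adjusted contrast 10% and the change contrast 5%.

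**The case against.** The strongest reply is that efficacy is tertiary, described as exploratory and limited, and tied to no decision rule. The Design paragraph and the tertiary aim, which follow outcomes from baseline onward, also point towards differential change, so the main effect may never have been meant to judge DSS. This stands as to weight: the feasibility aim is untouched. It does not rescue the power statement, because group-by-time has 66% at 86 with the plan's own d and r.

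That shortfall is conditional. Group-by-time reaches 82% at N = 86 if d = 0.60, which is within the cited range, and 81% at N = 96 if r = 0.6. This is fair, but those are not the inputs the plan states, and a fading effect moves power the other way. The main effect misses 80% throughout the cited range of d at r = 0.50 and throughout r = 0.3 to 0.7 at d = 0.50.

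The remaining objections concern the remedy. Preferring change scores to adjustment is a judgement. If a 0.20 SD baseline gap shrank to 0.10 at follow-up, the adjusted contrast would reject 5% and the change contrast about 8%. With one facility per arm, neither separates DSS from facility-specific change. The replacement powers also assume independent participants although DSS is taught in groups of 12. With an assumed intraclass correlation of 0.02 in both arms, 75% becomes about 68%. All of this stands. It is why the contrast below is an example, shown with the other, and why every restated figure needs its caveats.

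**Conclusion.** The concern holds. Among the standard calculations tried, 86 is returned only by the group main effect, and it gives 80% power only if the arms differ by an average of 0.50 SD over three occasions, one of them before DSS. For a difference of 0.50 SD at both follow-ups and none at baseline, neither group term of the planned ANOVA reaches 80%, at 86 or at 96. The shortfall at 86 is about 34 percentage points for the main effect and 14 for group-by-time.

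These figures rest on the plan's d = 0.50 and r = 0.50, and on assumptions the documents do not state: equal baselines, a constant effect, the same correlation between all pairs of measures, and independent participants. The main-effect result is robust to d and r over the ranges shown; the group-by-time result is not. This should be fixed because the plan claims a power that its design and analysis do not deliver. Its reach is limited to how Aim 3 is interpreted and used to plan the next study.

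**What to change.** 1. In the Aim 3 sentence of Statistical strategy, state that DSS will be judged by a baseline-referenced group contrast, not by the group main effect. One suitable choice is the between-arm difference in change from baseline to the mean of the two follow-ups. Report the baseline-adjusted difference in the follow-up mean as a sensitivity analysis, because allocation is by facility.
2. In Justification of Sample Size, name the chosen contrast and replace the claim of 80% at 86. At d = 0.50 and r = 0.50 the change contrast has about 75% at 86 and 80% at 96. If group-by-time is kept, the figures are 66% and 71%. Say that these assume a constant effect and independent participants, and that the figure at 96 assumes no attrition.
3. Keep N at 96. Do not headline the roughly 90% of the adjusted contrast: it depends on equal baselines, which this design cannot assure.

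The cost is two rewritten sentences, with no extra participants, visits or data. The change and adjusted results may differ and both must be shown, and the stated power becomes somewhat less favourable than 80% at 86.

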To allow for a control group in this feasibility study, the PI will recruit 96 participants from two male facilities. Forty-eight persons will be enrolled from the treatment facility (Cybulski correctional institution) and forty-eight from the designated control facility (Osborne Correctional). Persons housed in these prisons have received or are completing an assigned sentence, may be directly released from the facilities to the community or half-way houses. One facility houses slightly less inmates but both have similar ethnic, and racial distributions. Nurses in the two facilities are contracted to provide nursing care to the inmate population and function under the same policies and procedures. Although there is no evidence to support the exact number of persons for Group patient education, the Center for Medicare and Medicaid has recommended 2-20 participants with an average of 10 participants (Health Care Finance Administration, 2000). Attrition rates for diabetes self-management education (DSME) programs vary as do the number of sessions for various group DSME models. Attrition rate for individual and group DSME has been reported from 0-50% (Newman, Steed, & Mulligan, 2004). In consideration of attrition, twelve participants will be enrolled in each of the four sessions.

To further reduce attrition rates, the PI will send appointment reminders to participate in a sealed envelope via the Connecticut Department of Corrections (CTDOC) mail system. This process will be accomplished in cooperation with the CDOC liaison.

1. Health Care Finance Administration, rules and regulations. Fed Regist 65:83129–83154, 2000

If applicable, how many potential participants will be screened?

When screening procedures are conducted as part of the consent process, participants that fail to screen will be counted as being enrolled in the study.

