
Participants in the DSS treatment or Control group may be transferred to another correctional facility or released from prison before the end of the DSS program. As a result of these unplanned events, the participant may feel disappointed about not being able to complete the program.
	
The DOC will communicate with the PI about impending transfers or early release dates. For transfers, the DOC will ask the participant if he would prefer to delay transfer until the end of the DSS. If not, the PI will meet with the participant prior to or after transfer to provide all of the education materials and answer any questions. If the participant is to be released from prison earlier than anticipated, the PI will meet with participant prior to discharge to provide all of the education materials associated with the 6-DSS sessions and answer their DSS related questions.
	
Moderate
	
Minimal

Although incarcerated persons are used to being on waitlists for CDOC programming or other usual care services, potential or enrolled participants in the control group may be frustrated with waiting 12 weeks for the DSS intervention.
	
Potential participants who will be assigned to the control group may decline participation in the study if they do not want to wait for participation. Enrolled participants may withdraw from the study at any time and will be told this during informed consent.
	
Minimal
	
Minimal

--	--	--	--

Economical Risks:	Procedures to Protect Against / Minimize Risks	Likelihood of Occurrence	Seriousness to Subject if Risk Occurs
None	NA	NA	NA

Social Risks:	Procedures to Protect Against / Minimize Risks	Likelihood of Occurrence	Seriousness to Subject if Risk Occurs
Inmates may feel uncomfortable if others in the facility know they are participating in a research study.	All measures will be taken to ensure a participant's privacy and no information will be disclosed to any third parties without the participant's permission. All research personnel are certified in meeting HIPAA requirements.	Minimal	Minimal to Moderate

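### Aim 3's repeated-measures ANOVA uses only men with all three surveys although loss is foreseen; a mixed model would keep the partial data, and power drops below 80% only if more than about 10% of men are incomplete

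*Combined protocol and SAP*

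**What the plan says.** The Statistical strategy (Section VII) gives one sentence on the Aim 3 analysis: the effect on the outcome variables "will be evaluated with repeated-measures ANOVA and for the assumptions of repeated measures ANOVA". The software sentence is "Data will be analyzed using SPSS". Nothing in the document defines the participants analysed, the handling of a missing survey, or a sensitivity analysis.

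The sample-size section assumes a standardised difference of 0.50 at the 5% level, with "power 0.80, 2 groups, and an estimated moderate correlation (0.50) between 3 repeated measures", and reports that "the power analysis 25 indicated a need for 86 participants". It enrols 96 to allow for attrition of up to 10% and expects 5-10%. It also cites 20-50% for diabetes education programmes elsewhere and says that no attrition data exist for prisons.

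Several routes to a missing survey are foreseen:
- The risk table says participants in either group "may be transferred to another correctional facility or released from prison before the end of the DSS program", and rates the likelihood as moderate. It offers those men materials and answers to questions, but mentions no survey.
- The sample-size section names movement between facilities and lockdown.
- The eligibility section lists removal for segregation, hospital stay or illegal behaviour.
- In the treatment facility, Measure 2 is completed during session 6, and no make-up visit is described.

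There is one direct safeguard. Measure 3 is taken at six weeks after the programme, "or immediately before release if release from prison is less than 6 weeks post-DSS program".

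**The concern.** Conventional repeated-measures ANOVA needs a full set of three scores from each man. A man who completes Measures 1 and 2 and is then transferred contributes nothing. The document does not state this deletion; it follows from the named method.

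Two things are at stake. The first is precision, if more men are incomplete than the 96 allows for. The second is validity. Men lost through transfer, release or segregation need not resemble those who stay, and the arms are whole facilities, so loss may differ between them. The results are meant to refine the intervention and inform a later pilot study, so a distorted effect would carry forward. A Measure 3 taken early also departs from the common measurement times that the ANOVA assumes.

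**Working it through.** **Inputs from the sample-size section.** d = 0.50, so f = d/2 = 0.25 for two equal groups; alpha 0.05; m = 3 measures; correlation rho = 0.50; 86 needed; 96 enrolled (48 per facility).

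**Reproducing 86.** For the between-groups effect, the noncentrality is lambda = N x f² x m / (1 + (m - 1) x rho), with 1 and N - 2 degrees of freedom. At N = 86: lambda = 86 x 0.0625 x 3 / 2 = 8.06 and power is 0.801. At N = 84 it is 0.792. The plan's figure reproduces, and 86 / 0.90 = 95.6, rounded up to 96. A group-by-time interaction with f = 0.25 would need only 28, so 86 is sized for the between-groups effect averaged over the three measures.

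**Power by share of incomplete men.** The last column is a likelihood mixed model on all available surveys. It assumes d = 0.50 at every measure, equal correlations of 0.50, and incomplete men split equally between one and two surveys completed.

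| Men missing any survey | Complete cases of 96 | Complete-case power | Mixed-model power |
|---|---|---|---|
| 5% | 91 | 0.824 | 0.840 |
| 10% | 86 | 0.803 | 0.835 |
| 20% | 77 | 0.755 | 0.827 |
| 30% | 67 | 0.696 | 0.818 |
| 50% | 48 | 0.547 | 0.799 |

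(Power uses the unrounded number, for example 86.4 at 10%.) With 85 complete cases power is 0.797, so the margin is 96 - 86 = 10 men, or 10.4%.

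**Baseline-to-Measure-3 change.** The variance of a change is 2 x (1 - 0.5) = 1 SD². At 10% loss there are 43.2 men per arm, so SE = sqrt(2 / 43.2) = 0.215 SD. Power for a 0.50 SD difference is 0.63 with complete cases and 0.65 with the mixed model; at 20% loss it is 0.58 and 0.61.

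**Bias, as illustration only.** Both loss mechanisms are assumed. The true effect is 0.50 SD at Measures 2 and 3 and zero at baseline, so the true average over three measures is (0 + 0.50 + 0.50) / 3 = 0.33.
- *Treated men with lower baseline scores are lost more often* (odds multiplied by e per SD, at each follow-up). A base rate of 10% per follow-up gives about 24% loss in the treatment arm, and 20% gives about 39%. The completer difference in change is 0.39 and 0.32. At the 10% base rate the averaged difference moves the other way, to 0.48. An all-data likelihood analysis returns 0.50 for the change.
- *Treated men with lower Measure 2 scores more often miss Measure 3; control loss is random.* At 10%, 20% and 30% loss the completer change at Measure 2 is 0.55, 0.59 and 0.63. The averaged difference is 0.39, 0.45 and 0.50. The baseline-to-Measure-3 change stays at 0.50.

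**The case against.** The strongest reply is that attrition is already paid for, and on power at the plan's own rate this stands. A reader might infer that the analysis is underpowered even under the plan's assumption, by applying 10% loss separately to Measures 2 and 3: 96 x 0.9² = 78 complete cases and power 0.76, or at 20% each, 96 x 0.8² = 61 and power 0.65. The document does not support this. Its 10% is a single overall allowance, and those cases are 19% and 36% total loss. A man transferred before Measure 2 would usually miss Measure 3 as well, so the losses overlap rather than multiply.

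The plan also limits loss. Men enrol 6-9 months before release and the last survey is at week 15 (105 days, about three and a half months). Transfer may be delayed to the end of the programme if the man prefers, reminders and evening sessions are planned, and the pre-release Measure 3 rescues data. These reduce the problem but do not close it: the transfer delay does not extend to Measure 3, and no survey is described for men who leave before the programme ends.

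Finally, Aim 3 is tertiary, the protocol calls efficacy testing limited, and attrition is itself a feasibility outcome. That bears on the weight of the point, not on the choice between two methods of nearly equal cost.

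**Conclusion.** The point holds in a limited form. The named method discards partial data in a setting where the plan itself expects partial data, and a better method is available in the same software.

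- **Power.** It is adequate at the plan's 5-10%. It falls below 80% only above about 10% incomplete, reaching about 0.76 at 20% and 0.55 at 50%. Those rates lie in the range cited for other programmes; whether they would occur in these prisons is unknown. The figures assume equal loss in the two arms and the plan's own effect size and correlation.
- **Bias.** It is possible if loss depends on observed scores or differs by facility. A reader might infer from one simulation that the effect would be understated. The documents do not support a direction or a size: the same mechanism lowers the change contrast and raises the averaged one, and another mechanism leaves the baseline-to-Measure-3 change untouched.
- **Gain.** The main benefit is keeping partial data and remaining valid when loss depends on observed scores. The power gain is sizeable only for the averaged effect. Confounding by facility remains, and so does any bias from loss that depends on unobserved scores.

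This change should be made, but it does not threaten the primary feasibility aim.

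**What to change.** In the Aim 3 paragraph of the Statistical strategy, replace repeated-measures ANOVA with a linear mixed model for repeated measures (SPSS MIXED):
- include every available survey from every enrolled man;
- fit group, time and group-by-time, with an unstructured covariance across the three measures;
- take the group-by-time contrasts at Measures 2 and 3, relative to baseline, as the effects of interest;
- repeat the analysis with the actual survey date as time, to cover Measure 3 taken early;
- report the number of men missing each survey, by reason and by facility.

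State that the model relies on loss being explained by observed data, and that it does not adjust for differences between the two facilities. The cost is a few sentences in the statistical section: same software, no new data and no change to enrolment.
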